2 STUDY DESIGN

This is a multicenter, randomized, open-label, Phase 3 long-term safety study of topically applied sofpironium bromide gel, 5% and 15% in subjects with axillary hyperhidrosis.

A maximum of 300 subjects, at approximately 30 clinical sites, will be enrolled to obtain approximately 150 subjects that have completed 12 months of dosing and clinical assessments.

Subjects will be randomized 1:2 to receive either sofpironium bromide gel, 5% or 15% (100 subjects dosed with 5% gel and 200 subjects dosed with 15% gel). Subjects will apply the investigational product once daily at bedtime, to their axillae for 12 months.

Vital signs and adverse events will be collected at each visit. Local tolerability assessments (including burning, itching, dryness, scaling, and erythema assessed using standardized scales) will be collected at each post-Screening visit. Blood and urine samples will be collected and analyzed at Screening and then Weeks 4, 12, 24, 36, and 48 for routine hematology, chemistry, and urinalysis parameters. Additionally, a urine pregnancy test (UPT) for females of child-bearing potential will be collected and analyzed at each visit except at Week 2 (Visit 3), Week 6 (Visit 5), and Week 52 (Visit 17). Patient-reported outcomes HDSM-Ax, PGI-S, PGI-C, and DLQI will be recorded during the study at predefined time points. HidroQoL will be recorded at baseline, Week 2, and Week 6; only the first 100 subjects enrolled in the study will complete this assessment.

A total of 17 scheduled visits will take place over approximately 52 weeks. See Section 7.1 for an events table of this study.

3 STUDY OBJECTIVES AND ASSESSMENTS

The purpose of this Phase 3 study is to assess the long-term safety, local tolerability, and efficacy of sofpironium bromide gel, 5% and 15% when applied topically in subjects with axillary hyperhidrosis.

3.1 **Study Objectives**

Primary:

To evaluate the long-term safety and local tolerability of sofpironium bromide gel, 5% and 15% when applied topically in subjects with axillary hyperhidrosis.

Secondary:

- To evaluate the long-term effect of topically applied sofpironium bromide gel, 5% and 15% on HDSM-Ax in subjects with axillary hyperhidrosis.
- To evaluate the long-term effect of topically applied sofpironium bromide gel, 5% and 15% on DLQI in subjects with axillary hyperhidrosis.

Other:

To evaluate the effect of topically applied sofpironium bromide gel, 5% and 15% on HidroQoL in subjects with axillary hyperhidrosis.

3.2 Study Assessments

Safety Measures:

The following safety assessment measures will be conducted to evaluate the long-term safety and local tolerability of sofpironium bromide gel, 5% and 15%:

- Adverse events
- Local tolerability assessments including burning, itching, dryness, scaling and erythema
- Vital signs (blood pressure, pulse rate, respiratory rate, and temperature)
- Laboratory tests (hematology, chemistry, and urinalysis) and pregnancy testing in FOCBP

Efficacy Assessments:

The following assessment measures will be conducted to evaluate the long-term efficacy of sofpironium bromide gel, 5% and 15%:

- HDSM-Ax as measured by the subject
- DLQI as measured by the subject for subjects ≥ 17 years of age
- Patient Global Impression Scales^{*}; Severity (PGI-S)^{**} and Change (PGI-C)[†]

* these questions will be included in the HDSM-Ax questionnaires

** administered with each administration of the HDSM-Ax

 † administered at Visit 10 (Week 24) and end of treatment Visit 16 (Week 48) only

Additionally, HidroQoL assessment will be conducted as an exploratory analysis, as measured by the subject (for subjects \geq 17 years of age). This assessment will be performed at baseline, Visit 3 (Week 2), and Visit 5 (Week 6) for only the first 100 subjects enrolled in the study.

4 STUDY POPULATION

4.1 Number of Subjects

A maximum of 300 subjects, at approximately 30 clinical sites, will be randomized to receive either 5% or 15% sofpironium bromide gel in a 1:2 ratio to obtain approximately 150 subjects (50 subjects dosed for 48 weeks with 5% gel and 100 subjects dosed for 48 weeks with 15% gel) who have completed 12 months of dosing and clinical assessments.

4.2 Inclusion Criteria

Subjects must fulfill all of the following criteria to be eligible for study admission:

- 1. Male or female subject ≥ 12 years of age in good general health.
- 2. Diagnosis of primary axillary hyperhidrosis in the opinion of the Investigator that meets all the following criteria:
 - a. HDSM-Ax of 3-4 inclusive at both of the Screening visits (Visit 1) and Baseline Visit (Visit 2).
 - **b.** Symptoms of axillary hyperhidrosis for ≥ 6 months' duration prior to Baseline Visit (Visit 2)
- **3.** The ability to understand and sign a written informed consent form (ICF), which must be obtained prior to any study-related procedures (including medication wash-out, if required) and treatment. Subjects less than the age of consent must sign an Assent for the study and a parent or a legal guardian must sign the informed consent (if the subject reaches age of consent during the study they should be re-consented at the next study visit).
- 4. The ability to understand and sign a Health Insurance Portability and Accountability Act (HIPAA) authorization form which shall permit the use and disclosure of the subject's individually identifiable health information.
- 5. The ability to understand and follow all study-related procedures including study drug administration.
- 6. Sexually active females of childbearing potential (FOCBP)* must agree to periodic pregnancy testing and use a medically acceptable method of contraception while receiving protocol-assigned product. Acceptable contraceptive methods include the following:
 - **a.** Abstinence for the duration of the study, or where partner is sterile (e.g., vasectomy), is an acceptable form of contraception;
 - **b.** Hormonal contraception, including oral, injectable, or implantable methods started ≥2 months prior to screening; OR
 - c. Two forms of non-hormonal contraception, including intrauterine devices (IUD; ≥1 week status post placement), or properly used barrier methods (e.g., male or female condoms, cervical cap/diaphragm, spermicidal agents).

* FOCBP for this study includes any premenopausal female capable of becoming pregnant who has not undergone successful surgical sterilization (hysterectomy, bilateral tubal ligation [\geq 6 months prior to baseline] or bilateral oophorectomy) or is not postmenopausal (defined as amenorrhea >12 consecutive months in women \geq 55 years of age).

4.3 **Exclusion Criteria**

Meeting any of the following criteria will exclude a subject from participating in this study:

- 1. In the Investigators opinion, any skin or SC tissue conditions of the axilla(e), (i.e., the axillary area should be deemed otherwise "normal", besides the hyperhidrosis diagnosis, and free of blisters, large boils or sinus tracts, significant scarring or open wounds).
- 2. Prior use of any prohibited medication(s) or procedure(s) within the specified timeframe for the treatment of axillary hyperhidrosis:
 - a. Botulinum toxin to the axillary area within 6 months of the Baseline Visit (Visit 2).
 - **b.** Axillary thermolysis, sympathectomy or surgical procedures of the axillary area at any time in the past.
 - c. Serotonergic agonist (or drugs that increase serotonin activity including Selective serotonin reuptake inhibitors [SSRIs]), beta-blocker, alpha-adrenergic agonist (clonidine), dopamine partial agonist or tricyclic antidepressant treatment within 28 days of the Baseline Visit (Visit 2). However, if a subject has been on a stable dose (in the opinion of the PI) of any of these medications and has not had a recent change in hyperhidrosis frequency or severity for 3 months prior to the Baseline Visit; they may be included. Doses of these agents should not be altered during the course of the study.
 - d. Any topical prescription treatment for hyperhidrosis within 15 days of Baseline Visit (Visit 2).
- **3.** Anticholinergic agents used to treat conditions such as, but not limited to, hyperhidrosis, asthma, incontinence, gastrointestinal cramps, and muscular spasms by any route of administration (e.g., intravenous [IV], oral, inhaled, topical, etc.) within 28 days of the Baseline Visit (Visit 2).
- 4. Use of potent oral inhibitors of cytochrome P450 CYP3A & CYP2D6 and transporter inhibitors (OCT2/MATE1/MATE2) within 14 days prior to the Baseline Visit (Visit 2). The use of topical antifungal medications is permitted if not applied in the treatment area. See Appendices 6 and 7.
- **5.** Any oral or topical homeopathic or herbal treatment (i.e., alternative therapies such as sage tablets, chamomile, valerian root and St. John's Wort) within 7 days of the Baseline Visit (Visit 2).
- 6. Use of any cholinergic drug (e.g., bethanechol) within 15 days of the Baseline Visit (Visit 2).
- 7. Use of any anti-anxiety and/or anti-depressant, amphetamine product or drugs with known anticholinergic side effects is prohibited with the following exceptions:
 - **a.** If a subject has been on a stable dose of an anti-anxiety and/or anti-depressant drug and has not had a recent change in hyperhidrosis frequency or severity for 3 months; they may be included.
 - **b.** An amphetamine product may be allowed if the dose has been stable for ≥ 6 months without change in hyperhidrosis frequency or severity.
 - c. Drugs with known anticholinergic side effects (taken within the last 28 days) including dry mouth, blurred vision may be allowed based on the Investigator's assessment.

NOTE: If anticholinergic side effect(s) are experienced on these medications prior to starting study medication; document the side effect(s) and severities in the source document and the eCRF. The doses of these agents should not be altered during the course of the study.

8. Known cause of hyperhidrosis or known history of a condition that may cause hyperhidrosis (i.e., hyperhidrosis secondary to any known cause such hyperthyroidism, diabetes mellitus, medications, etc.).

- 9. Subjects with hyperhidrosis symptoms initiated or exacerbated with menopause.
- **10.** Subjects with unstable type 1 or type 2 diabetes mellitus or thyroid disease, history of renal impairment, hepatic impairment, malignancy, glaucoma, intestinal obstructive or motility disease, obstructive uropathy, myasthenia gravis, benign prostatic hyperplasia (BPH), neurological conditions, psychiatric conditions, Sjögren's syndrome, Sicca syndrome, or cardiac abnormalities that may alter normal sweat production or may be exacerbated by the use of anticholinergics in the Investigator's opinion.
- **11.** Known hypersensitivity to glycopyrrolate, anticholinergics, or any of the components of the topical formulation.
- 12. Subject is pregnant, lactating or is planning to become pregnant during the study.
- **13.** Participating in a study or used an investigational drug or device within 28 days prior to the Baseline Visit (Visit 2).
- 14. Any major illness within 28 days before the Baseline Visit (Visit 2).
- **15.** Any other condition, including psychiatric illness (depression and/or anxiety) that would interfere with study participation and/or evaluation of study endpoints or laboratory abnormality that, in the opinion of the Investigator, would put the subject at unacceptable risk for participation in the study or may interfere with the assessments included in the study.
- **16.** History or presence of supraventricular tachycardia, ventricular arrhythmias, atrial fibrillation or atrial flutter.
- **17.** Employees of Brickell Biotech, Inc., the Investigator, or contract research organization (CRO) involved in the study, or an immediate family member (partner, offspring, parents, siblings, or sibling's offspring) of an employee involved in the study.

5 INVESTIGATIONAL PRODUCT (IP)

Sofpironium bromide gel is an anhydrous gel formulation containing the drug substance in a gel base comprising hydroxylpropyl cellulose National Formulary (NF), hexylene glycol NF, isopropyl myristate NF, citric acid anhydrous United States Pharmacopeia (USP), and alcohol dehydrated USP. Sofpironium bromide gel is a clear to slightly translucent colorless gel and is packaged in a white colored, metered pump container. One pump container is packaged in a carton with 2 applicators. The total gel volume in each pump container is ~50 mL (~43 g). The gross weight of each full container at baseline is approximately 78 to 84 grams.

Based on one full pump actuation delivering ~0.67 mL of the gel formulation, a total of approximately 38 mL of gel is required for 4 weeks (28 days) of daily dosing to the axillae. Therefore, each pump container is sufficient for \geq 28 days of dosing per protocol instructions. A new container will be dispensed to each subject at Baseline and then Weeks 4, 8, 12, 16, 20, 24, 28, 32, 36, 40, and 44.

5.1 Storage of Investigational Product

The investigational product must be stored in a secure area with access limited to the Investigator and authorized site staff and administered only to subjects entered into the clinical study, at no cost to the subject, in accordance with the conditions specified in this protocol.

Investigational product should be stored at controlled room temperature 68°F to 77°F (20°C to 25°C) with excursion permitted between 59°F to 86°F (15°C to 30°C). Maintenance of a temperature log (manual or automated) is required.

5.2 Instructions for Use and Administration of Investigational Product

Investigational product kit cartons will be provided to each site and will include one individual plastic pump container per each carton. Each carton will also contain 2 applicators. An investigational plastic pump container will contain sufficient drug product for a 28-day treatment period.

Each carton will have a unique identifier number printed on the label and the pump container label will display the same unique identifier number.

Each subject will be randomized via an Interactive Response Technology (IRT) system to receive either sofpironium bromide gel, 5% or 15% to topically apply, once daily at bedtime, to each axilla using the supplied applicators for 48 consecutive weeks. Instructions on the use of the IRT system will be provided in a separate manual.

Subjects will be instructed to apply the investigational gel product to each axilla using all the gel expressed from ONE FULL ACTUATION of the pump per each axillary dose application. Each full actuation of the pump corresponds to approximately 0.551 grams for the 5% and 0.576 grams for the 15% investigational product.

The subject will apply all doses of investigational product at night, prior to going to bed using the supplied applicators. Subjects will apply their first dose of gel prior to bedtime on the night of their Baseline Visit. The subject will be instructed to continue applying the investigational product each night with the last application to occur the night before attending the end of-treatment evaluation (i.e., Week 48, Visit 16). Subjects should wash the applicator each night after dosing. Two applicators are provided in each kit to compensate for loss or damage during handling; it is not necessary to use all the applicators over the specified dosing interval.

To ensure accurate dosing, the study staff will be instructed to first prime and then weigh each pump container before dispensing to the subject. Priming is accomplished by fully pressing the pump for five (5) sequential actuations; the dispensed gel from these 5 priming actuations is considered waste and should be discarded.

The weight of the pump container, with the cap on, will be recorded for the uniquely numbered container after priming and can then be dispensed to the subject. Over the course of the study, a container will be primed/weighed/dispensed at each of the Baseline Visit (Day1) and then Weeks 4, 8, 12, 16, 20, 24, 28, 32, 36, 40, and 44 (Visits 4-15) for a total of 12 containers. Each of the 12 containers previously dispensed will be returned by the subject at the next respective visit, weighed and weight recorded per the unique bottle number. At the End of Treatment visit (Week 48), the subject will bring the 12th container to his/her visit for the final weight determination, however, no additional investigational product will be dispensed. Study subjects may return the applicators, or they may discard them after dosing is completed.

At each visit, gel application instructions and compliance will be discussed and documented.

5.3 **Instructions for the Subjects**

Subjects will be instructed to apply the investigational product every day, at night prior to bedtime using a supplied applicator as follows (a written instruction sheet, and access to a study product application video and digital mobile application will be supplied to the Subject):

1. Expose the underarm areas and ensure they are dry. Do not wash the underarm areas for at least 30 minutes prior to application.

- 2. Hold the plastic applicator between the index and middle fingers and the thumb of the left hand. Carefully, by applying consistent pressure to the actuator with an index finger, dispense the gel of ONE FULL actuation onto the dome of the white plastic applicator.
- 3. Immediately apply study product to the right underarm area.
- 4. Distribute all the gel expressed using the plastic applicator in a way that covers all the underarm area where the hair grows by gently applying a layer of the product.
- 5. Repeat the procedure to apply the study product to the left underarm using the right hand.
- 6. Wash both hands and the plastic applicator thoroughly for about 2 minutes.
- 7. Allow the study product to dry for 5 minutes before putting any clothes on the upper body.

Important information:

- The subject should sleep in a T-shirt or similar pajama to avoid touching the underarm area while sleeping.
- Subjects should maintain their underarm areas grooming habits but should not shower, shave, or wash the underarm area for at least 8 hours after study product application. If the subject takes a shower, shaves or washes the underarm area at night then it should be at least 30 mins before study product application. Ensure the underarm areas are dry prior to application of the study product.
- Subjects should not apply any other product to the axillary area (including deodorant) for at least 8 hours after study product application.
- The subject should use the applicator provided to avoid contact with skin of the hands. Special care should be taken to avoid contact of the gel with the eyes or mouth. Of note, hands should be washed after applying the gel to avoid possible skin and eye contact with the gel.
- The study product contains alcohol and is flammable. The subject should avoid fire, flames or smoking during the application and until the gel has dried. The subject should not expose the container to fire, flames or extreme heat.

6 CONCOMITANT MEDICATIONS/TREATMENTS

Information on concomitant medications/treatments (e.g., aspirin, Tylenol, birth control pills, IUD, vitamins) taken during study participation, or which may require a washout for study participation will be recorded. Every effort should be made to keep dosing with any concomitant medications consistent/constant during the study.

6.1 **Permissible Medications/Treatments**

Therapy considered necessary for the subject's welfare may be given at the discretion of the Investigator. If the permissibility of a specific medication/treatment is in question, the Medical Monitor should be contacted.

Subjects will be instructed to not apply any contraindicated topical product to their axillary area (see list in Section 6.2). Deodorant should not be applied within 8 hours following the application of study product (suggest applying in the morning).

6.2 **Prohibited Medications/Treatments**

The decision to administer a prohibited medication/treatment is made with the safety of the study participant as the primary consideration. When possible, Brickell Biotech's Medical Monitor should be notified before a prohibited medication/treatment is administered.

Prior to the inclusion of a subject in the study, as specified in Sections 4.2 and 4.3 (I/E criteria), and throughout the duration of the study, the use of the following medications/treatments is prohibited:

- Anticholinergic agents used to treat conditions such as, but not limited to, hyperhidrosis, asthma, incontinence, gastrointestinal cramps, and muscular spasms by any route of administration (e.g., IV, oral, inhaled, topical including topical glycopyrrolate or derivatives).
- Any oral or topical homeopathic or herbal treatment (i.e., alternative therapies such as sage tablets, chamomile, valerian root and St. John's Wort).
- Any prescription topical products, including topical prescription antiperspirants or similar agents (e.g., Drysol, Xerac AC, Certain DRI) and hand sanitizers applied to the axillae for the duration of the study.
- Any treatment or procedure for axillary hyperhidrosis including but not limited to:
 - botulinum toxin
 - thermolysis treatments including microwave (e.g., MiraDry), laser or other(s)
 - o sympathectomy
- Any surgical procedure involving the axillae (including laser hair removal), or any surgical procedures that will result in significant scarring of the axillae.
- Any oral cholinergic (e.g. bethanechol) throughout the duration of the study.
- Addition of, or change of dose for any medication that is allowed as specified in Sections 4.2 and 4.3 (I/E criteria) including serotonergic agonists (or drugs that increase serotonin activity including SSRIs), beta-blockers, alpha-adrenergic agonist (clonidine), dopamine partial agonists, tricyclic antidepressants, anti-anxiety and/or other anti-depressant drugs, amphetamine products and drugs with known anticholinergic side effects.

Since no drug-drug interaction studies have been conducted to evaluate whether concomitant medications affect sofpironium bromide, potent inhibitors of CYP3A and, CYP2D6 and transporter inhibitors (OCT2/MATE1/ MATE2) should not be administered as specified in Sections 4.2 and 4.3 (I/E criteria): see Appendices 6 and 7.

7 **PROCEDURES**

The timing of each assessment is listed in the Time and Events Table (Section 7.1).

Each subject will report for 17 distinct visits (over 52 weeks).

All Screening assessment results must be completed and reviewed prior to the Baseline Visit (within 31 days). Therefore, none of the Screening Visit days can occur on the same day as the Baseline Visit.

Subjects may be consented for up to 31 days before the Baseline Visit. Subjects outside this screening window shall be re-consented and certain screening activities may need to be repeated. Prior to enrollment into the treatment phase of the study, the Investigator or designee will contact the Medical Monitor to address such subjects on a case-by-case basis.

7.1 **Time and Events Table**

VISIT	1	2	$3 - 6^{1}$	7 – 16 ²	17 ³
Time Point	Screening (-31 to 0 Days)	Baseline (Day 1)	Weeks 2, 4, 6, 8 ±3 days	Q4 Weeks (Weeks 12 – 48) ±5 days	End of Study Week 52 ±5 days
			PROCEDURE		
Informed Consent	X				
Medical Hx, Demog	X				
I/E Criteria	X	X			
Randomization		X			
РЕ	X				X
Vitals (BP, HR, RR, Temp)	X	X	X	X	х
HDSM-Ax	X	X	Х	x	Х
PGI-S ⁴	X	X	Х	X	X
PGI-C ⁵				X	
DLQI ⁶		X	Х	X	
HidroQoL ⁷		X	Х		
Local Tolerability ⁸		x	Х	X	X
Adverse Events ⁸	X	X	Х	X	X
UPT (FOCBP) ⁹	X	X	Х	X	
IP Dispensation/ Return/ Resupply ¹⁰		X	Х	X	
IP Weight ¹⁰		X	X	X	
Compliance Training/Evaluation		X	X	X	X
Safety Labs (heme., chem., urine) ¹¹	X		X	X	
Conmeds	X	X	Х	X	X

Abbreviations: BP = blood pressure; Chem. = chemistry; Conmeds = concomitant medications; DLQI = Dermatology Life Quality Index; FOCBP= females of child-bearing potential; HDSM-Ax = Hyperhidrosis Disease Severity Measure-Axillae; heme. = hematology; HR = heart rate; Hx = history; I/E = inclusion/exclusion; IP = investigational product; PE = physical examination; PGI-C = Patient Global Impression of Change; PGI-S = Patient Global Impression of Severity; RR = respiratory rate; UPT = urine pregnancy test, urine = urinalysis.

¹No more than 14±3 days may elapse between Visit 2 (Baseline) and Visit 3 (Week 2).

²No more than 28±5 days may elapse between each of Visits 7-16 (Weeks 12-48).

³The End of Study Visit may occur ± 5 days of Week 52.

⁴Administered as Question #6 of HDSM-Ax at every assessment.

- ⁵Administered as Question #7 of HDSM-Ax at Week 24 and Week 48 visits.
- ⁶Administered at Baseline, Weeks 2, 6, 24, and 48.
- ⁷Administered at Baseline, Week 2, and Week 6; only the first 100 subjects enrolled in the study will complete this assessment.
- ⁸ Investigator local tolerability assessments to be performed after the Subject local tolerability assessments.
- ⁹ Performed at Screening, Baseline, and then Weeks 4, 8, 12, 16, 20, 24, 28, 32, 36, 40, 44, and 48.
- 10 Performed at Baseline and then Weeks 4, 8, 12, 16, 20, 24, 28, 32, 36, 40, 44, and 48.
- ¹¹ Performed at Screening and then Weeks 6, 24, and 48.

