Up to 300 subjects will be randomized to receive either sofpironium bromide gel, 5% or 15% in a ratio of 1:2 (100 subjects dosed with 5% gel and 200 subjects dosed with 15% gel).

11.2 **Compliance with Protocol**

At each post-baseline visit, the following activities will occur to ensure compliance with the protocol:

- Subjects will be asked if they have used the investigational product as instructed.
- Subjects will be reminded to perform ONE FULL pump actuation and use the gel expressed per application to each axilla and asked if they experienced any problems dispensing the investigational product.
- Subjects will be asked if they used any other products on their axillae.
- Site staff will review concomitant medication use since the previous visit and determine if any concomitant medication use qualifies as a protocol deviation
- At each post baseline visit until EOT, site staff will collect the dispensing container from the subject, then weigh and record the weight of the used container.

11.3 **Study Termination**

The study may be stopped at a study site at any time by the site Investigator, after first notifying the Sponsor and discussing the reason(s) for stopping the study. Brickell Biotech, Inc. may stop the study with appropriate notification.

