4. ANALYSIS POPULATIONS

Identification of the subjects to be included in each analysis population will be determined and finalized prior to database lock. Subjects will be classified into the Safety, Intent-to-Treat (ITT), Per Protocol (PP), and HidroQoL (HQL) populations according to the following definitions:

Safety Population

The Safety Population will include all subjects randomized in the study who received study drug at least once. Subjects will be included in the treatment group based on the majority of actual treatment they received (even if not the treatment group to which they were randomized).

ITT Population

The ITT Population will include all subjects who were randomized. Subjects will be included in the treatment group to which they were randomized, regardless of the treatment received.

PP Population

The PP Population will be a subset of the ITT Population and will include subjects who meet the following criteria:

- Meets the inclusion/exclusion criteria
- Has not taken or applied any interfering concomitant medications.
- Completed the following visits:
 - o Visit 1 (Screening) and the required HDSM-Ax data collection
 - o Visit 2 (Baseline) and the required HDSM-Ax data collection
 - o Visit 4 (Week 4), and the required HDSM-Ax data collection
 - o Visit 7 (Week 12), and the required HDSM-Ax data collection
 - o Visit 10 (Week 24), and the required HDSM-Ax data collection
 - o Visit 16 (Week 48), and the required HDSM-Ax data collection
 - o Visit 17 (Week 52), and the required HDSM-Ax data collection
- Treatment received per randomization assignment

HOL Population

The HQL Population will be used for HidroQol analyses. Subjects with "Yes" noted for the question "Subject flagged for the Baseline-Visit 5 HidroQol Protocol" on the Subject CRF page are included. The first 100 subjects \geq 17 years of age enrolled were eligible for this population.

Version: 1.0 Page 17 of 51

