8.3 Analysis Methods

All secondary and other efficacy endpoints will be summarized using descriptive statistics by treatment group for the ITT and PP populations. For continuous measures, mean, standard deviation, median, minimum and maximum will be reported for results at time point and for change from baseline by visit as indicated in Section 8.2.1. For categorical measures, frequency and percentage of subjects will be reported by the visits indicated in Sections 8.2 and 8.2.1. The exploratory HidroQoL endpoint will be summarized by treatment group as a continuous measure using descriptive statistics. At each visit, both domain scores and the total score will be summarized for the HQL population. No formal hypothesis testing or modeling of efficacy endpoints will be performed. Figures for proportion of subjects achieving ≥1-point, ≥1.5-point, and ≥2-point imprpovment in HDSM-Ax (for both 7-Item and 11-Item) by visit will be provided. Additionally, figures of mean change from baseline over time for HDSM-Ax (for both 7-Item and 11-Item) will be provided.

Version: 1.0 Page 24 of 51

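### Non-prescription antiperspirants have no single status in the protocol, and the ITT HDSM-Ax responder rates have no rule for scores recorded after an added sweat-reducing treatment

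*Protocol*

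**What the plan says.** **Protocol rules on axillary products**

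- Section 4.3, exclusion 2d, sets a 15-day washout for topical hyperhidrosis treatment, limited to prescription products.
- Section 6.2, topical item, prohibits "Any prescription topical products, including topical prescription antiperspirants or similar agents". It goes on to give product examples and to mention hand sanitizers on the axillae. It does not define what counts as similar.
- Section 6.2, next item, prohibits "Any treatment or procedure for axillary hyperhidrosis including but not limited to" a short list of procedures.
- Section 5.3, repeated in Appendix 5, says: "Subjects should not apply any other product to the axillary area (including deodorant) for at least 8 hours after study product application".
- Section 6.1 says: "Deodorant should not be applied within 8 hours following the application of study product", and suggests the morning instead.
- Section 11.2, for every post-baseline visit: "Subjects will be asked if they used any other products on their axillae".

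No section names non-prescription antiperspirants.

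**SAP rules on scoring**

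- Section 4, ITT: "Subjects will be included in the treatment group to which they were randomized, regardless of the treatment received".
- Section 8.1.4 sets the end-of-treatment value as the Visit 16 (Week 48) score, and 8.1.1 imputes nothing for efficacy.
- Section 8.3: "All secondary and other efficacy endpoints will be summarized using descriptive statistics by treatment group for the ITT and PP populations".
- The PP set in Section 4 leaves out subjects with interfering concomitant medications. It also requires HDSM-Ax data at Screening, Baseline and Weeks 4, 12, 24, 48 and 52.
- Section 5.2 names on-study prohibited medication as a possible major violation. No section links it to efficacy scoring.

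**The concern.** HDSM-Ax asks about underarm wetness and damp clothing since waking the day before. A sweat-reducing product applied in the morning acts inside that window. Both arms receive active gel, there is no vehicle arm, and the reported result is each arm's change from its own baseline. Randomisation therefore does not remove the effect of an added product from the within-arm figures.

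Over 48 weeks, a subject who does poorly on the gel has a motive to add something. If that subject then crosses a responder threshold, the ITT table credits the gel. Because the product's status is unclear, sites may also classify the same behaviour differently, which affects who is recorded as a violator and who leaves the PP set. What is at stake is the reading of the 48-week responder rates. The primary safety objective is not affected by this scoring gap.

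**Working it through.** **1. One behaviour, four rules.** Take a subject who uses a non-prescription antiperspirant each morning, more than 8 hours after the gel.

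| Source | Status of that use |
|---|---|
| Exclusion 2d | Not covered (prescription only) |
| 6.2 topical item | Unclear: framed around prescription products, with an undefined extension to similar agents |
| 5.3, Appendix 5 and 6.1 | Implicitly allowed after 8 hours; 6.1 mentions deodorant only |
| 6.2 next item | Prohibited on a plain reading, because the list is open-ended |

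**2. What happens to the score.** Suppose a subject starts a sweat-reducing product between Week 24 and Week 48 and attends Week 48.

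- ITT: the Week 48 score is used as observed. SAP 4, 8.1.1, 8.1.4 and 8.3 contain no rule that changes this.
- PP: the subject is removed only if the product is judged to be an interfering medication, a term neither document defines. If so, the visits before the product was started are lost too.

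**3. Size.** The plan states no response rate, usage rate, effect size or power, so there is no sponsor figure to reproduce on this point. The stated numbers of subjects are consistent: 300 at 1:2 is 100 and 200, and 150 completers at 1:2 is 50 and 100. The inputs below are assumptions.

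- f = share of subjects with a Week 48 score who added a product: 5% to 20%.
- d = rise in their probability of response due to it: 0 to 0.5.
- e = extra HDSM-Ax points due to it: 0.5 to 1.0.

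Overstatement of the responder rate = f × d:

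| f | d = 0 | d = 0.25 | d = 0.5 |
|---|---|---|---|
| 5% | 0 | 1.25 points | 2.5 points |
| 10% | 0 | 2.5 points | 5 points |
| 20% | 0 | 5 points | 10 points |

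Overstatement of mean improvement = f × e, from 0.05 × 0.5 = 0.025 to 0.20 × 1.0 = 0.20 HDSM-Ax points.

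The same calculation can start from non-responders. Let p be the true ≥1-point rate, let a = 10% to 30% of non-responders start a product, and let 30% of those cross the line. The overstatement is (1 − p) × a × 0.30.

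- p = 60%: 0.40 × 0.03 = 1.2 points to 0.40 × 0.09 = 3.6 points, so 61.2% to 63.6% is reported.
- p = 40%: 0.60 × 0.03 = 1.8 points to 0.60 × 0.09 = 5.4 points, so 41.8% to 45.4% is reported.

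**4. Direction.** Use that does not change from before Baseline affects both scores and need not bias the difference. No washout is stated for non-prescription products. If a share g used one at Baseline that lowered their score by e, and then stopped, mean improvement is understated by g × e. With g = 5% to 20% and e = 0.5 to 1.0, that is again 0.025 to 0.20 points, in the opposite direction.

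**5. Scale.** At a 50% response rate the 95% half-width is 1.96 × √(0.25/50) = 13.9 points for 50 completers, and 1.96 × √(0.25/100) = 9.8 points for 100.

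**6. Effect of counting users as non-responders.** The rate falls by f × the users' observed response rate. With f = 5% to 20% and a users' rate of 50% to 100%, the fall is 0.05 × 0.50 = 2.5 points to 0.20 × 1.00 = 20 points. It is small only if use is rare.

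**The case against.** The case on the other side is substantial.

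- **Existing guards.** Section 6.2 already prohibits other hyperhidrosis treatment throughout the study, 5.3 asks subjects to keep their grooming habits, and 6.1 sends doubtful products to the Medical Monitor. Site staff judge whether concomitant use is a deviation (11.2). The SAP tabulates major violations and concomitant medications and plans PP versions of the secondary and other efficacy endpoints. All of this stands. A reader might infer that nothing stops a subject from starting a product after Baseline, or that the plan ignores such use. The text contradicts both.
- **Discontinuation.** Section 7.4 lists non-compliance with procedures and an exclusion criterion becoming apparent during the study. Either could cover prohibited treatment. This stands too, but it does not settle how scores are handled in subjects who stay.
- **Inflation is not shown.** This is correct. There are no usage data, and the direction is not fixed. Entry also requires HDSM-Ax of 3 to 4 at both Screening and Baseline, so a subject already using such a product qualifies only if still severe on it.
- **Difference between strengths.** A reader might infer more added use on the 5% gel. The protocol's own efficacy summary describes the dose groups as essentially equivalent on patient-reported measures, so the documents do not support that.
- **Legitimate choice.** Observed-score ITT alongside PP is an acceptable descriptive presentation. This stands, and for that reason the planned tables should be kept.
- **Versions.** The SAP follows protocol Amendment 4 and the protocol supplied is Amendment 01. Section 6.2 may have been changed since.

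These points leave two gaps open: the conflicting status of non-prescription antiperspirants, and the missing ITT scoring rule. PP does not close the second. Its key term is undefined, a non-prescription antiperspirant may not be classed as a medication, and the set also requires completion of Weeks 48 and 52.

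**Conclusion.** The concern holds in a limited form. The protocol passages give conflicting signals on non-prescription antiperspirants and must be reconciled. The ITT responder rates count scores after an added or prohibited sweat-reducing treatment as response to gel, and with no vehicle arm nothing in the trial shows how much that contributes.

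The 48-week response could be overstated if poor responders start such products. The stronger statement, that it is inflated, is not supported. The size is unknown: 0 to 10 percentage points rests entirely on assumed use of 5% to 20% and an assumed rise of 0 to 0.5 in response probability. That range is mostly below the sampling half-widths for 50 and 100 completers, although a bias does not shrink as the sample grows. Efficacy is secondary, descriptive and untested, and no sample size calculation depends on it, so this is a minor improvement.

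**What to change.** 1. **Protocol.** Reconcile exclusion 2d, Section 5.3 (with Appendix 5), Section 6.1 and the two items in 6.2 so that non-prescription antiperspirants have one stated status. Which status is for the sponsor to decide. Check the wording against Amendment 4 first.
2. **Data.** Record the question already asked under 11.2 as a dated eCRF item. Where that is no longer possible, existing concomitant medication dates can serve for products recorded there.
3. **SAP 8.3.** Keep the planned ITT tables. Add a supplementary version of the ≥1, ≥1.5 and ≥2-point responder tables in which visits on or after the start of a new hyperhidrosis treatment count as non-response. Identify these from dated records. Under SAP 9.1.1 a wholly missing date becomes the treatment start date, which would turn every post-baseline visit into a non-response, so the rule should say how undated records are handled.

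Do not add a version of the continuous change that simply omits those visits. If poor responders are the ones who add products, omission removes them selectively and can raise the mean improvement.

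**Cost:** protocol wording, one eCRF field, and a few repeat runs of existing tables. The supplementary responder rates will be lower than the planned ones, slightly so if use is rare.
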